APPENDIX III REPORTING SELECTED LABORATORY PARAMETERS IN CONVENTIONAL UNITS

All clinical laboratory parameters will be reported in the International System (SI) units as standard practice. In addition, descriptive statistics for values and changes from baseline in conventional units at all assessed visits will be reported for selected laboratory parameters as listed in [Table 20-1](#) below.

Table 20-1. List of Selected Parameters to be Reported in Conventional Units

Number	Laboratory Parameter	Conventional Unit
1	Alanine Aminotransferase (SGPT)	U/L
2	Albumin	G/dL
3	Alkaline Phosphatase	U/L
4	Aspartate Aminotransferase (SGOT)	U/L
5	Bilirubin, Direct (Conjugated)	mg/dL
6	Bilirubin, Indirect (Unconjugated)	mg/dL
7	Bilirubin, Total	mg/dL
8	Blood Urea Nitrogen	mg/dL
9	Calcium	mg/dL
10	Cholesterol, HDL	mg/dL
11	Cholesterol, LDL	mg/dL
12	Cholesterol, LDL direct and calculated (combined) (This lab parameter could be the same as #11)	mg/dL
13	Cholesterol, Total	mg/dL
14	Creatine Kinase	U/L
15	Creatinine	mg/dL
16	Glucose	mg/dL
17	Insulin	uIU/mL
18	Triglycerides	mg/dL
19	Uric Acid	mg/dL
20	Hemoglobin	G/dL

Patient narratives will also include the values in conventional units for the selected lab parameters. That might be accomplished by presenting the values in conventional units within the parentheses next to the values in SI units.

APPENDIX IV ANALYSES SPECIFIED FOR ABBREVIATED CSR

On 14 DEC 2020, FDA provided Type C Written Response in which they agreed to release Allergan of the postmarketing requirement (PMR 2947-9) to conduct Study RGH-MD-24, based on new information obtained since initial Vraylar approval in SEP 2015. Study RGH-MD-24 was thus early terminated. The analyses for the abbreviated CSR are the subset of analyses specified in the SAP and listed below. The details are provided in the corresponding SAP sections.

Patient disposition and analysis populations

- Summary of screen failure patients and the associated reasons for failure
- Summary of patient disposition during OLTP and DBTP respectively
- Summary of analysis populations

Demographics and other baseline characteristics

- Summary of demographic and other baseline characteristics, and baseline efficacy variables
- Summary of prior and concomitant medications

Efficacy analyses

- Primary efficacy analysis
- Analyses of change from baseline in the PANSS total score during OLTP and DBTP
- Analyses of change from baseline in BACS composite score

Extent of exposure

- Summary of exposure during OLTP, DBTP and entire study

Safety analyses

- Overall summary of AEs during OLTP, OL Safety Follow-up, DBTP, and DB Safety Follow-up
- Summary of TEAEs during OLTP, OL Safety Follow-up, DBTP, and DB Safety Follow-up

- Summary of treatment-related TEAEs during OLTP and DBTP
- Summary of TEAEs leading to premature discontinuation of IP during OLTP and DBTP
- Summary of ocular events during OLTP, OL Safety Follow-up, DBTP, and DB Safety Follow-up
- Summary of TESAEs during OLTP, OL Safety Follow-up, DBTP, and DB Safety Follow-up
- Summary of TESAEs of ocular events during OLTP and DBTP
- Summary of laboratory PCS during OLTP and DBTP
- Summary of CSSRS during OLTP and DBTP

The following listings will be provided for the abbreviated CSR

- Patients with TEAEs leading to premature discontinuation of IP
- AEs for patients with TEAEs leading to premature discontinuation of IP
- Patients with ocular events
- AEs for patients with ocular events
- Patients who died
- AEs for patients who died
- Patients with SAEs
- Patients with laboratory PCS during OLTP and DBTP
- Patients who meet potential Hy's law criteria during OLTP and DBTP
- Patients with suicidal ideation or behavior
- Patient disposition
- Patients who discontinued OLTP or DBTP
- Patients with protocol deviations

- Demographics and other characteristics at baseline/randomization
- Medical and surgical history
- Prior and concomitant medications
- Psychiatric history
- OL/DB dosing data
- IP compliance during OLTP and DBTP
- Plasma concentration
- Relapse status
- Efficacy data analyzed for the abbreviated CSR
- BACS
- Adverse events
- Clinical laboratory results and comments
- Vital signs
- ECG results and overall interpretation
- Ophthalmologic examination and lens status
- CSSRS
- Patients with study visits impacted by COVID-19

APPENDIX V SUMMARY OF CHANGES FOR AMENDMENT 1

Amendment #1 specifies the following changes to the Statistical Analysis Plan for Study RGH-MD-24 dated 12 Feb 2019. The major changes are summarized below:

1. Specified the subset of analyses for abbreviated CSR in Appendix IV
2. Planned a listing of patients with visits impacted by COVID-19 in Section 18.0
3. Provided the rationale of performing a subset of planned analyses in the abbreviated CSR at the beginning of Section 4.0
4. Modified the definition of OL SFU population in Section 6.4
5. Modified the definition of DB ITT population in Section 6.5
6. Modified the definitions of OLTP and DBTP at the beginning of Section 7.1
7. Specified that the percentage of patients in each analysis population would be provided in Section 7.1
8. Specified the definitions of baseline efficacy variables for OLTP and DBTP respectively and planned summary for them respectively in Section 8.0
9. Removed the analysis of BACS composite Z score due to the reason that this value would not be derived by vendor that performs the BACS data analysis in Section 10.3
10. Specified that the OL baseline CGI-S value would be served as the baseline value for CGI-I in Section 10.3
11. Specified the descriptive statistics for safety continuous and categorical variables respectively in Section 11.0
12. Specified the summary of TEAEs during SFU would be separated as OL SFU and DB SFU respectively in Section 11.1
13. Specified the summary of common TEAEs would be separated as OLTP and DBTP respectively in Section 11.1
14. Removed the summary for patients with TEAEs leading to discontinuation if these occurred in 5 or more patients in Section 11.1
15. Specified the summary of patients with any EPS SAEs, and EPS SAEs, and EPS AEs leading to premature discontinuation of IP would be overall during OLTP and by treatment during DBTP in Section 11.1

16. Specified that for the summary of selected clinical laboratory parameters in conventional units, only patients with selected clinical laboratory data at baseline and at least one postbaseline visit during OLTP and DBTP will be included in the summary in Section 11.2
17. Specified that the summary of patients with orthostatic hypotension would be provided for OLTP and DBTP in Section 11.3

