The use of placebo control is critical to the study design both to understand the safety findings of the drug and to ensure that efficacy results can be interpreted. In this study, the placebo control is used during the DB treatment period to demonstrate the reemergence of symptoms of schizophrenia upon withdrawal of cariprazine compared with patients who continue cariprazine treatment. Patients who continue cariprazine treatment should maintain improvement in their schizophrenia symptoms for a longer period of time when compared to those switched to placebo. Patients switched to placebo should have an earlier return of symptoms of schizophrenia.

The fixed-dose design during the DB treatment period was selected to maintain patients at the cariprazine dose level at which their symptoms of schizophrenia had responded. The dose selected, 4.5 mg/d, represents a dose that has been proven to be efficacious in schizophrenia while minimizing side effects. The lower dose during the DB treatment period was

determined following an FDA request to include doses lower than those used to achieve a response in the acute phase, while maintaining a dose within the approved range for that indication (1.5 to 6.0 mg/d). If both doses prove to be effective in preventing relapse, an evaluation will be made to see if a lower dose also achieves better tolerability during the maintenance phase of treatment.

The duration of the DB treatment period, with a maximum of 26 weeks, was selected to provide sufficient time to demonstrate schizophrenia relapse upon withdrawal of cariprazine. The 4-week safety follow-up (SFU) period allows continued patient monitoring after investigational product (IP) has been discontinued.

2 Study Objectives and Clinical Hypotheses

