11.0 SAFETY ANALYSES

The safety analyses will be performed for the OL safety, OL SFU and DB safety populations. The summarization will be overall for the OLTP in the OL safety population and OL SFU period in the OL SFU population, and by treatment group for the DB period and the DB SFU period in the DB safety population. The summarization for the OLTP will use the OL safety population as the denominator. The summarization for the DBTP will use the DB safety population as the denominator. The summarization for the OL SFU period or DB SFU period will use the OL SFU population or the DB safety population as the denominator respectively.

Safety parameters will include adverse events (AEs), clinical laboratory parameters, vital signs, Electrocardiographic (ECG) parameters, ophthalmological parameters, Columbia–Suicide Severity Rating Scale (C-SSRS), and EPS scales, including Abnormal Involuntary Movement Scale (AIMS), Barnes Akathisia Rating Scale (BARS), and Simpson-Angus Scale (SAS).

For each safety parameter, the last assessment made before the first dose of OL IP will be used as the baseline for all analyses of that safety parameter, unless stated otherwise. Continuous variables will be summarized by number of patients and mean, SD, median, minimum, and maximum values. Categorical variables will be summarized by number and percentage of patients.

The derived visits in the DBTP will use the same strategy as described in Section 10.0. The detailed week mapping windows is provided in Section 16.1.

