11.7.1 Extrapyramidal Symptom Scales

A patient will be considered to have treatment-emergent parkinsonism if the patient's SAS score was ≤ 3 at baseline and > 3 at any postbaseline assessment. A patient will be considered to have treatment-emergent akathisia if the patient's BARS score was ≤ 2 at baseline and > 2 at any postbaseline assessment. The number and percentage of patients with treatment-emergent parkinsonism or akathisia will be tabulated. Listings of patients with treatment-emergent parkinsonism or akathisia will be provided, including the PID number, baseline and postbaseline values. Listings of all AEs for patients with treatment-emergent parkinsonism or akathisia will also be provided.

Descriptive statistics (n, mean, SD, minimum, median, and maximum) for EPS scale parameters (AIMS, BARS, and SAS) and changes from baseline values at each assessment timepoint in this study will be presented overall for the OLTP and by treatment group for the DBTP.

12.0

HEALTH OUTCOMES ANALYSES

Not applicable.

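### SAP Appendix IV gives every safety domain an output except the EPS rating scales, so the abbreviated CSR would omit scale-defined akathisia and parkinsonism

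*SAP*

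**What the plan says.** SAP 11.0 lists the safety domains. It begins "Safety parameters will include adverse events (AEs), clinical laboratory parameters, vital signs, Electrocardiographic (ECG) parameters, ophthalmological parameters" and goes on to the C-SSRS and the three EPS scales (AIMS, BARS and SAS), which makes seven.

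SAP 11.7.1, following Protocol 7.3.4.5.1, defines two outcomes from scale scores. Parkinsonism is treatment-emergent if the SAS score is at most 3 at baseline and above 3 at any later assessment. Akathisia is treatment-emergent if the BARS score is at most 2 at baseline and above 2 later. The planned output is explicit: "The number and percentage of patients with treatment-emergent parkinsonism or akathisia will be tabulated". Listings of the affected patients, listings of their adverse events, and descriptive statistics for all three scales are also planned.

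Appendix IV then sets the scope of the abbreviated CSR: "The analyses for the abbreviated CSR are the subset of analyses specified in the SAP and listed below". Its safety tables include "Summary of TEAEs during OLTP, OL Safety Follow-up, DBTP, and DB Safety Follow-up" and "Summary of laboratory PCS during OLTP and DBTP", and a set of listings follows. AIMS, BARS and SAS appear in neither part.

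**The concern.** A shortened report after termination is legitimate, and Appendix IV drops many planned tables. For the other safety domains, though, the reduction stops at a listing or better. Vital signs and ECG lose their tables but keep listings. Only the EPS scales lose everything. The BACS, an additional efficacy scale, keeps both an analysis and a listing.

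Both study objectives include safety. AIMS, BARS and SAS are the trial's scheduled, rater-scored measures of movement side effects. With neither a table nor a listing, a reader of the report could not derive scale-defined akathisia or parkinsonism for any treated patient.

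**Working it through.** **Step 1: the number of scheduled assessments.** Protocol 6.5.8.1 places the EPS scales at Visits 2, 3, 7, 9, 11, 13, 15, 17, 19, 21, 23 and 26/ET, which is 12 visits. The visit-by-visit procedures agree:

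- Protocol 8.4.2: Visit 2 (1)
- Protocol 8.4.3: Visits 3, 7, 9, 11 (4)
- Protocol 8.4.4: Visit 13 (1)
- Protocol 8.4.5: Visits 15, 17, 19, 21, 23 (5)
- Protocol 8.4.6: Visit 26/ET (1)

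1 + 4 + 1 + 5 + 1 = 12. Visit 2 is the baseline, so 12 − 1 = 11 assessments can show emergence. This is a maximum. A patient randomized at Week 14 has Visit 13 procedures in place of Visit 11, which leaves 11 assessments, 10 of them postbaseline. Patients who discontinue usually have fewer still.

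**Step 2: SAP 11.0 domains against Appendix IV.**

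| Domain in SAP 11.0 | Table in Appendix IV | Listing in Appendix IV |
|---|---|---|
| Adverse events | Yes | Yes |
| Laboratory | Yes (PCS values) | Yes |
| Vital signs | No | Yes |
| ECG | No | Yes |
| Ophthalmology | Ocular-event tables | Yes (examination and lens status) |
| C-SSRS | Yes | Yes |
| EPS scales (AIMS, BARS, SAS) | No | No |

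Six of the seven domains have at least one output. If the ocular-event tables are set aside as adverse-event tables, ophthalmology still has its examination listing and the count does not change.

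**Step 3: is a reason given?** SAP 17.0, on changes from the protocol analyses, covers only the adverse-event time frame and the SAE definition. Section 4.0 and Appendix V explain why there is a subset at all, but not why this domain was left out. Item 15 of Appendix V revises the EPS adverse-event summaries of SAP 11.1. It does not mention the scales, and those EPS summaries are not carried into Appendix IV either.

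**Step 4: what would still be reported.** Akathisia or parkinsonism recorded as an adverse event would appear in the TEAE summaries and the adverse-event listing. EPS rescue drugs would appear in the concomitant-medication summary and listing. What is lost is the SAS-based and BARS-based outcomes and all AIMS data.

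**The case against.** The strongest reply is that abbreviation was deliberate. The postmarketing requirement was released, and the SAP says openly that it reports a subset. Much else is not named in Appendix IV, including CGI-S change, CGI-I, PSP, hypertension shifts, orthostatic hypotension and the QTc tables. How far to abbreviate is partly the sponsor's choice. EPS that mattered clinically should leave a trace as adverse events or rescue medication. Protocol 4.8.3.2 asks for the three scales before EPS rescue is dispensed, except in medical urgency. Output specifications are in a separate document that is not available here.

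Much of this stands, and it limits the point to the scale data. It does not remove the gap. The other dropped safety tables belong to domains that keep at least a listing. Adverse-event preferred terms do not reproduce the score-based definitions. Appendix IV, not the separate specifications, sets the report's scope.

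A reader might infer more than the documents support:

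- **That akathisia and parkinsonism would go wholly unreported.** They would not, as Step 4 shows.
- **That a promised comparison of tolerability between doses is being abandoned.** Protocol Section 1 does say "an evaluation will be made to see if a lower dose also achieves better tolerability", but only if both doses prove effective. After early termination, nothing shows that this evaluation is still owed. The point rests on the general safety objectives.
- **That the "Plasma concentration" listing in Appendix IV supports this point.** Protocol 6.3 says pharmacokinetics are not applicable, so that line needs reconciling. It is a separate clerical matter and says nothing about EPS.
- **That the omission was an oversight.** The documents do not state intent.

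**Conclusion.** The point holds for the rater-scored EPS data. The EPS scales are the one safety domain of seven without any output in Appendix IV, and no specific reason is given. Followed as written, the abbreviated CSR would omit scale-defined treatment-emergent parkinsonism and akathisia and every AIMS result, from up to 12 scheduled assessments per patient (at most 11 postbaseline).

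The loss cannot be sized in patients. The plan was for 1035 open-label patients and 345 randomized, but the number treated before termination is not stated. The conclusion assumes that Appendix IV is a closed list, as its opening says. This is an inexpensive completeness correction to safety reporting. The primary efficacy analysis is unaffected.

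**What to change.** Add to Appendix IV:

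1. The SAP 11.7.1 table of treatment-emergent parkinsonism and akathisia, overall for the OLTP and by arm for the DBTP.
2. The SAP 11.7.1 listings of patients who meet either definition, and of their adverse events.
3. Preferably, a by-patient listing of AIMS, BARS and SAS scores, to match the listings kept for vital signs and ECG.

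Items 1 and 2 are already specified. Item 3 is a new output: SAP 11.7.1 lists only patients who meet a definition, and it gives AIMS descriptive statistics but no emergence criterion and no listing. Without item 3, or the AIMS descriptive statistics, AIMS would remain unreported.

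If the omission was intended, state the reason in SAP 17.0 and keep at least a listing. The cost is a small amount of extra programming and a slightly longer report. No new data are needed.

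Separately, reconcile the plasma concentration line with Protocol 6.3.
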